### **When does it start?**

The first in-person training will be July.

The second in-person training and 10-week telephone training will start late summer/early fall.

### **I have trouble with transportation. Does that matter?**

Most of the Living Well with Diabetes program is done over the phone. We can arrange transportation for training.

### **I only have a cell phone. Is this OK?**

You will receive an UAB cell phone for use for the study.

### **How much travel will I need to do?**

You will need to attend the 2-day training in person.

You will have to meet with your community coordinator regularly to receive / turn in study materials.

**Thank you for your interest in this study. It is our hope that by working together we can design innovative and effective ways to manage the burden of diabetes in Alabama’s Black Belt.**

**If not interested, please find out reasons for not wanting to participate:** *(check all that apply)*

- Transportation Difficulties
- Do not want to become a UAB employee
- Don’t have enough time
- Other: *(specify)*

**If not interested, please find out if there is anyone else the person would like to refer to become a peer advisor:**

Name:	Phone:	Relationship:
Name:	Phone:	Relationship:
Name:	Phone:	Relationship:

**INCLUSION CRITERIA: Who are we looking for to become peer advisors?**

To be invited to participate in the study, peer candidates must answer “Yes” to all questions in the gray squares. Questions in the white squares are “informational” and are other important characteristics/information to consider when interviewing Peer Advisor Candidates.

If you have any questions or concerns about someone, please reach out to the other community coordinators, [name], [name], and/or [name].

1. Do you have a desire to help others?	 Yes  No																												
2. Are you willing to become an UAB employee?	 Yes  No																												
3. Do you have diabetes or do you help a close friend or family member take care of their diabetes?	 Yes, I have diabetes  Yes, I have diabetes and I care for someone with diabetes  No, I do not have diabetes, but I care for someone with diabetes  No, I do not have diabetes and I do not care for someone with diabetes																												
4. Do you have a doctor that you see regularly for your medical care?	 Yes  No if yes, who/city_____																												
5. Do you have a doctor that you see for your diabetes or other medical care?	 Yes  No if yes, who/city_____																												
6. Do you take pills every day that were prescribed by a doctor? Do you help a close friend or family member with their pills that were prescribed by a doctor? (For example: pills for diabetes, high blood pressure, high cholesterol)	 Yes, I take pills.  Yes, I take pills and I help someone with their pills  No, I don't take pills, but I help someone else with their pills  No, I don't take pills and I do not help someone else with their pills.																												
7. Are you willing to attend and complete the Peer Advisor training? Training will consist of 2 in-person training days, and 10 weeks of training over the telephone.	 Yes  No																												
8. Are you willing to work with 5-7 clients over 5 months, by telephone, at first weekly, and then biweekly and monthly?	 Yes  No																												
9. Are you willing to attend weekly group phone calls with other peer advisors and study doctors?	 Yes  No																												
10. For every client you take on, you will need to spend about 1 hour a week scheduling calls, completing the program, and completing paperwork. This will be weekly for the first 2 months and then biweekly and monthly for the last 3 months. Most peer advisors choose to take 3-5 clients at a time. In addition to your client calls, you will generally have 2 meetings every week or every 2 weeks. Both meetings together will last 30 minutes. You will meet with UAB staff one-on-one for about 30 minutes per week. On a scale from 1 to 10, 1 being not confident at all to 10 being very confident, how confident are you that you will have enough time for the project?	
 
 not confident		very confident	
 
 1	2	3	4	5	6	7	8	9	10		
 
	not confident										very confident			1	2	3	4	5	6	7	8	9	10					
not confident										very confident																			
1	2	3	4	5	6	7	8	9	10																				
11. On a scale from 1 to 10, 1 being not easy and 10 being very easy, how easy is it for you to listen to other people?	
 
 not easy		very easy	
 
 1	2	3	4	5	6	7	8	9	10		
 
	not easy										very easy					1	2	3	4	5	6	7	8	9	10			
not easy										very easy																			
1	2	3	4	5	6	7	8	9	10																				
12. Have you volunteered on other research projects as a peer advisor (sometimes referred to as community health advisor, community health worker, etc.)?	 Yes  No																												
12.1. If yes, please provide the name of those projects, describe your role, length of time of your participation, and whether you are still volunteering on that project:	If yes, please provide, Project name: Length of time of participation: Whether you are still volunteering:																												

13. What other community volunteer activities do you currently do?	
14. How long have you lived in the present community in which you reside?	Community: Time:

 
• We would like to ask you about your personal views about medicines in general.
 
• These are statements other people have made about medicines in general.
 
• Please indicate the extent to which you agree or disagree by saying if you strongly agree, agree, are uncertain, disagree, or strongly disagree.
 
• There are no right or wrong answers. We are interested in your personal views.
 
	
15. Doctors use too many medicines	 Strongly agree  Agree  Uncertain  Disagree  Strongly Disagree
16. People who take medicines should stop their treatment for a while every now and again	 Strongly agree  Agree  Uncertain  Disagree  Strongly Disagree
17. Most medicines are addictive	 Strongly agree  Agree  Uncertain  Disagree  Strongly Disagree
18. Natural remedies are safer than medicines	 Strongly agree  Agree  Uncertain  Disagree  Strongly Disagree
19. Medicines do more harm than good	 Strongly agree  Agree  Uncertain  Disagree  Strongly Disagree
20. All medicines are poisons	 Strongly agree  Agree  Uncertain  Disagree  Strongly Disagree
21. Doctors place too much trust on medicines	 Strongly agree  Agree  Uncertain  Disagree  Strongly Disagree
22. If doctors had more time with patients they would prescribe fewer medicines	 Strongly agree  Agree  Uncertain  Disagree  Strongly Disagree
23. Give page 4 of the screening form to the peer advisor candidate. Being a peer advisor for this study will require a lot of writing and reading. I would like for you to complete the following page.	How long did the peer candidate take to complete the task?  Did the peer candidate have any trouble completing the task? If yes, please provide details.

Now that we have shared our expectations for the project, we want to give you a chance to tell us why you decided to participate. Take a minute and write down the top 3 reasons why you are interested in becoming a Peer Advisor.

***I am interested in becoming a Peer Advisor because:***

1. \_\_\_\_\_  
\_\_\_\_\_  
\_\_\_\_\_  
\_\_\_\_\_  
\_\_\_\_\_  
\_\_\_\_\_  
\_\_\_\_\_

2. \_\_\_\_\_  
\_\_\_\_\_  
\_\_\_\_\_  
\_\_\_\_\_  
\_\_\_\_\_  
\_\_\_\_\_  
\_\_\_\_\_

3. \_\_\_\_\_  
\_\_\_\_\_  
\_\_\_\_\_  
\_\_\_\_\_  
\_\_\_\_\_  
\_\_\_\_\_

## Appendix C

### **Peer Advisor's Program Tools (Peer Advisor Manual)**

# Peer Advisor Manual

## Client Information

**UPDATE AS NEEDED**

- You will receive the name and study cell phone number of your client from your community coordinator or one of the research team members from UAB.
- Write them into the areas below. You'll get additional information during the first session call.
- You will call the client to set up the appointment for the first session.
- Try to have the first session within 7 days of receiving the client's name.

**Client name:**

**Study cell phone number:**

**Notes:**

**Home number:**

**Work number:**

*Additional people that would know how to get in touch with the client:*

**1. Phone number and the person at this number and how she/he is related to client:**

**2. Phone number and the person at this number and how she/he is related to client:**

- 
- You should have this information filled out based on information that the Living Well with Diabetes research assistants have already collected.
  - During the first call, fill in any missing information, especially additional phone numbers of people that might know how to get in touch with the client.
  - You will continue to update this information during the next 12 weeks.

**Scheduling Session 1**

**REMEMBER!** Session 1 should be within 7 days of receiving the client's name. If unable to reach the client, note your attempt(s) in the log below.

Call Log		
Dates	Times	Notes
Attempt 1		 no answer / phone busy  left message / voicemail  rescheduled  bad phone number**
Attempt 2		 no answer / phone busy  left message / voicemail  rescheduled  bad phone number**
Attempt 3		 no answer / phone busy  left message / voicemail  rescheduled  bad phone number**
Attempt 4		 no answer / phone busy  left message / voicemail  rescheduled  bad phone number**
Attempt 5		 no answer / phone busy  left message / voicemail  rescheduled  bad phone number**
Attempt 6		 no answer / phone busy  left message / voicemail  rescheduled  bad phone number**
Attempt 7		 no answer / phone busy  left message / voicemail  rescheduled  bad phone number**
Attempt 8		 no answer / phone busy  left message / voicemail  rescheduled  bad phone number**

**\*\*All phone numbers provided are disconnected or 8 call attempts made\*\***

1. Community coordinator notified (note date / time):
 
_____
 
date                      time
	
2. Community coordinator calls back with Next Steps:

---	---

- *If you do reach the client, follow the script below.*

- Hello, Ms. / Mr. (\_\_\_\_\_), I'm (\_\_\_\_\_), your peer advisor from the Living Well with Diabetes Program.
- I'll be working with you during the next six months to help you with the program. Is this a good time for a five-minute call? *If not, schedule a time to call the client back.*
- Great! When you met the research assistant for this program, she asked you a lot of questions and checked your blood pressure and other things.
- She also left with you an Activity Book, DVDs and a DVD player, and your study phone. You watched the first session on the DVD at that time.
- Now, I'd like to set up an appointment to talk with you on the phone sometime this week for about 45 minutes. When would be a good time for that?

Date of Session 1:	Time:
---------------------------	--------------

- Let me give you my contact information in case you need to reschedule. If you don't mind grabbing your Activity Book, there is a place in the front where you can write my name and my phone number. *Let the client fetch the Activity Book and write your information.*
- OK, my name is (\_\_\_\_\_), and my phone number is (\_\_\_\_\_). If something comes up and you can't talk at the time we just scheduled, just give me a call and let me know, and we'll reschedule.
- Now, when we talk again, I'd like to go over the materials that the research assistant left with you. So, please have your Activity Book handy when I call. Also, you may want to re-watch the first session on the DVD.
- We're also going to talk briefly about your diabetes medications, so please have with you your diabetes medications in their pill bottles when we talk again.
- OK, I look forward to speaking with you then!

## Week 1, Session 1: “Introduction to Living Well with Diabetes”

**Session Goals:**

- Introduction to the program, review of schedule, commitment to the program
- Diabetes basics
- Setting a goal for diabetes medication taking
- Assign homework

**Before Calling the Client** -----

- From the in-person training, review the experiences that you, a family member, or someone you know have had while living with diabetes. Review client’s diabetes medications and medication barriers in client plan book.

**Reminder!!**

- Cover and check off all of the session content.
- Any text in GRAY BOXES is instructions for you: don’t read those sections aloud to the client.

Call Log			
	Dates	Times	Notes
Attempt 1			 no answer / phone busy  left message / voicemail  rescheduled  bad phone number**
Attempt 2			 no answer / phone busy  left message / voicemail  rescheduled  bad phone number**
Attempt 3			 no answer / phone busy  left message / voicemail  rescheduled  bad phone number**
Attempt 4			 no answer / phone busy  left message / voicemail  rescheduled  bad phone number**
Attempt 5			 no answer / phone busy  left message / voicemail  rescheduled  bad phone number**
Attempt 6			 no answer / phone busy  left message / voicemail  rescheduled  bad phone number**
Attempt 7			 no answer / phone busy  left message / voicemail  rescheduled  bad phone number**
Attempt 8			 no answer / phone busy  left message / voicemail  rescheduled  bad phone number**

**All phone numbers provided are disconnected or 8 call attempts made**	
1. Community coordinator notified (note date / time):  

 

 
 date time 
	2. Community coordinator calls back with Next Steps:  

## Getting to Know Your Client -----□

- Hello, Ms. / Mr. (\_\_\_\_\_), this is (\_\_\_\_\_) from the Living Well with Diabetes Program. How are you doing today?
- We had scheduled this time to talk for about 45 minutes. Is this still a good time?
- Great! Do you have your Activity Book and your diabetes medications in front of you? *If needed, let client fetch the Activity Book and medications.*
- OK, let's get started. First, let me make sure I have your contact information. I already have your study phone number, but in case it runs out of battery, would you give me the number of two people who would know how to reach you? *Verify that the information on page 1 of your manual is correct, and fill in any spaces that are empty.*
- Now, you may have questions between our sessions, so I want to make sure that you can call me. Do you still have my telephone number written on the front page of your Activity Book?
- If you do call me between our sessions, I might not be able to take your call all the time, but I'll call you back as soon as I can. Is that okay? *Make sure the client has your number written on the front page of the Activity Book.*
- Great. We will be talking today for about 45 minutes. Do you feel okay with that today?
- Wonderful. I would like to begin by getting to know each other better. Let me tell you a little about myself. 

### **Potential Talking Points**

- *Where you are from and where you live*
- *How long you and your family have lived in your area*
- *What you do for a living, or what you used to do if you are now retired*
- *How many children or grandchildren you have*
- *Whether you are married and for how long*
- *Your hobbies*
- *Your previous experience with the Encourage and Living Healthy programs and/or how you have been helping people with diabetes take care of their health*

- Can you tell me a little bit about yourself?

- *If needed, ask questions to get the client to open up.*
- *Write down some notes about things like their spouse's name, children's names, hobbies, etc.*
- *You will refer back to this section throughout the program.*

- Thank you for sharing that with me! I'm glad that we're getting to know each other better.

- An important part of this program is looking ahead positively. As part of that, would you mind sharing with me some things that you are looking forward to in the future, maybe a few years from now?

- *If needed, suggest events such as the wedding of a grandchild, the birth of a great grandchild, travel, or a special reunion.*
- *Try to get at least 2 to 3 long-term, meaningful events or goals that motivate them.*
- *Write goals on page 3 of the Client Plan Book.*

- Those are wonderful things to look forward to! This is the reason why I enjoy being a part of this program, because its goal is to help people like you and me live a full and healthy life.
- During this program, we'll discuss diabetes, healthy eating, exercise, and other health topics, providing information that can let you live longer, better.
- Now, it's very important that you understand that I am not a doctor or a nurse.
- I am a health coach, and I've been trained to work with you to complete this program. If you have a question that I can't answer, I will get the correct answer from the study doctors. How does that sound? *Let client answer.*

***Introducing the Living Well with Diabetes Program -----***

- Great, now that we know a little bit about each other, let's talk about the program, which is called, "Living Well with Diabetes."
- We know that diabetes is very common and has a big effect on how you live. You will be taking care of your diabetes for the rest of your life.
- There are a lot of things you need to do every day to take care of yourself when you have diabetes, but people with diabetes can still live a full and active life.
- So, this program will help you learn what to do to take care of yourself the best you can, every single day. You will learn these things through our discussions and watching videos.
- Speaking of the videos, when you first met the research assistant for this program, she left with you a DVD player and program DVDs, and you watched a video on this program.
- You will watch a video each week between our telephone sessions, so I want to make sure you're comfortable with the DVD player and the DVDs. Do you have any questions about the DVDs or how to use the DVD player?

*Refer to the FAQs for answers, or write down the question and let the client know that you will find out the answer and let them know next week.*

- OK, another item that you will use during the program is the Activity Book, which you have in front of you right now. During our sessions, we will learn about ways to live well with diabetes, and between sessions, we'll ask you to practice what you've learned.
- The Activity Book will help you practice, so let's turn to page 2. Here you can see some of the points made on the DVD. *Let your client get to the page.*

***Reviewing the DVD: Introduction to Living Well with Diabetes***-----

- What did you think about the video for this week? *Listen supportively.*
- Let's review. We learned that diabetes is a problem with the body's ability to handle blood sugar. When the blood sugar stays too high, it can cause all sorts of problems.
- The video also talked about why some people get diabetes and others don't, and how long it takes for most people to develop diabetes. What did you think about that? *Let the client answer.*
- Another thing the video talked about was the health problems that people with diabetes may experience. This is shown with the figure in the middle at the bottom of page 2. Do you see all the arrows pointing to different parts of the body that diabetes can affect? Can you remember some of those problems that diabetes can cause?

*If needed, remind your client that diabetes can cause blindness, stroke, heart attack, kidney failure, amputation, impotence, and nerve damage.*

- Was any of this information new to you? *Let the client answer and listen supportively.*
- There is a lot to take in, isn't there? For many people, learning that they have diabetes can be overwhelming at first.
- Do you remember the person in the video and what she went through when she first found out she had diabetes? What did you think about that? How did you feel when you first learned you had diabetes?

*Notes:*

- Thanks for sharing your experience with me! Different people react differently when they're first diagnosed, but most people find that living with diabetes has a big impact on their life.
- For most people, diabetes will never go away, so you'll need to manage your diabetes for the rest of your life. The good news is that there's a lot that you can do to keep your diabetes under control.
- An important point to remember is that much of what you should do to take care of your diabetes is good for everyone, not just people with diabetes. So, *your* healthy choices will not only help *you*, but it will also help the people that you care about.

- You will see that even small changes can have a big impact on your health and the health of the people around you. How do you feel about that? *Listen supportively.*
- You are making a wonderful start by joining this program! We have some easy ways to help you remember the important parts of taking care of your diabetes.
- OK, now find the box with “ABCDE” in it on page 2. The video also talked about the ABCDEs of diabetes. Do you remember what the ABCDEs stood for? *If needed, remind client the ABCDEs: A1c, or blood sugar; blood pressure; cholesterol; diet; and exercise.*
- Do you see the 3-legged stool, on the left-hand side of page 2, that the video talked about? Can you remind me what those 3 parts were? *If needed, remind client the 3 parts: healthy eating, being physically active, and taking medications as prescribed by the doctor.*

**Activity 1a: Checking for Side Effect or Cost Issues for Diabetes Medications -----**

- As we just talked about, taking medications is an important part of living well with diabetes. However, many people have trouble taking their medications, and there are a lot of reasons why this may be.
- I’d like to begin by focusing on the medications that you take for your diabetes and see if you have any questions. You told the research assistant what medicine you’re taking, and I’m looking at this list right now.

**Step 1.** Go to page 4 of the Client Plan Book, where UAB staff will have provided the names of all the diabetes medications your client is taking. Read out loud the name of the first diabetes medication.

- One medicine that you’re taking for your diabetes is [read off first diabetes medication if there is more than one].

**Step 2.** Ask how the client is taking the medication.

- Tell me how you take this medicine. How many times a day do you take it? How many pills each time? What are the times you take it?  
*Compare what the client tells you to what is written in the Client Plan Book for dose and frequency (and other directions, if any). For that medication, mark down whether the client is taking the medicine as directed by checking “Yes” or “No” in the column headed “Taking as Prescribed.” If they are not taking it correctly, explain how to take it. Then, have the client repeat back to you, at least once, how to take it correctly. Write notes in the space as needed so you can remember what the problem is. You’ll go over this in future sessions.*
  - Remember, once daily is usually in the morning at breakfast.
  - Twice daily is about 12 hours apart, morning and evening (for example, 8 a.m. and 8 p.m.)
  - Three times daily is about 8 hours apart (8 a.m., 4 p.m., midnight, or bedtime).

**Step 3.** Now ask about side effects for the first diabetes medication.

- Are you having any side effects from this medicine?

Check off “Yes” or “No” next to “Side Effects.”

If they say, “No” (they are not having a side effect), move on to Step 4.

If they say, “Yes” (they are having a side effect), then ask: What’s the side effect?

- Note down any side effects in the space provided in the client plan book. Then ask:

- Do you ever miss any doses of the medicine because of side effects?

- Check off “Yes” or “No” next to “Is the side effect causing missed doses?”
- Often people can live with minor side effects, so having a side effect doesn’t mean they aren’t able to take the medicine. If they say, “No” (they are taking the medicine even though they are having a side effect), praise them and move on to Step 4.
- If they say “Yes” (they are missing doses due to the side effect), tell them:

- Having side effects can make it hard for us to take our medicines! But, we are going to make a plan to see what we can do about that.

**Step 4.** Now ask about cost for the first diabetes medication.

- Are you having any trouble affording this medicine?

Check off “Yes” or “No” next to “Is medicine affordable?”

If they say, “No” (they are not having trouble affording the medicine), move on to Step 5.

If they say, “Yes” (they are having trouble affording the medicine), then say:

- OK, can you tell me more about this? In the client plan book, write down details about what makes it hard to afford this medication.
- Many people find it hard to afford their medicines! But, you and I are going to make a plan to see what we can do about that.

**Step 5.** Repeat Steps 1, 2, 3 and 4 for each diabetes medication.

**Step 6.** This step depends on what the client has told you during Steps 1-5 for each diabetes medication:

- If the client has trouble with side effects and/or cost,
  1. Complete Activity 1b, “Making a Plan for Side Effects and/or Cost Issues.”
  2. Then, go to Activity 2 and continue with the rest of the session.
- If the client does not have trouble with side effects and/or cost,
  1. Skip Activity 1b, “Making a Plan for Side Effects and/or Cost Issues.”
  2. Go to Activity 2 and continue with the rest of the session.

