## Participant Retention

During the 6 months of the trial, UAB staff will contact all participants 2-3 times. During these brief 5-minute calls, the staff will answer participant questions, update contact information, and provide help if needed in accessing study education materials. Participant retention plan will be a mixture of telephone and mail contacts as shown below:

Month	Control Participants	Month	Intervention Participants
1	Phone Call: Welcome to the study, answer questions	1	No contact
2	Postcard: Reminder to look at videos	2	Phone Call: answer questions, identify problems, update contact information
3	Phone Call: answer questions, identify problems, update contact information	3	No contact
4	Postcard: Keep in touch post card card	4	No contact
5	Phone Call: answer questions, identify problems, update contact information	5	Phone Call: answer questions, identify problems, update contact information
6	Postcard: reminder of upcoming data collection	6	No contact
All participants will receive postcards for birthdays, holiday cards (Thanksgiving, Christmas)			

During month 6 (control participants) or after the final session with the peer advisor (intervention participants), study staff will contact the participant to schedule their follow-up telephone interview and in-person data collection. Copies of postcards and telephone contact scripts are included in Appendix G.

The figure below shows the study flow from recruitment to the completion of the study.

LivingWell-FlowChart-v.2016-01-12

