## **Safety Assessments**

This study does not involve any new treatments of care, but rather focuses on standard care delivered in a new way. It is possible that the interventions will result in better compliance with medication treatment, resulting in over-control of diabetes or blood pressure. This could result in low blood sugar or low blood pressure and resultant symptoms. Therefore, we will monitor potential adverse events of this nature. We will monitor symptoms of low blood sugar in both trial arms at the follow-up data collection point as well as at ongoing contacts during the 12-week intervention phase, by peer coaches. During these contacts, symptoms of low blood sugar and low blood pressure will be assessed and reported to the investigators and to the participant's physician. If symptoms are present, the peer coach will refer participants to their primary care provider for evaluation immediately, assisting with the telephone call if needed.

Data on safety endpoints will be reviewed by a board convened for this purpose. Quarterly reports will be presented to the board over the course of the trial. The board will be constituted by 3 individuals experienced in the conduct of clinical trials and the safety of human subjects. Adverse events will be reported to the UAB IRB, and the NIH Office of Biotechnology Activities (OBA) in accordance with regulations, by the PI.

[name] and project investigators, including our community team members, will have an initial organizational meeting or conference call to discuss the protocol development, review of scientific, safety and ethical issues

related to the study design and approve plans for data integrity. After the initial planning meeting project investigators will be convened monthly in a meeting or conference call throughout the project period.

[name] will be responsible for monitoring the safety and efficacy of the study, executing the data and safety monitoring plan, and complying with the reporting requirements. She will provide a summary of the DSM report to PCORI on an annual basis as part of the progress report. The report will include participant's sociodemographic characteristics, expected versus actual recruitment rates, any quality assurance or regulatory issues that occurred during the past year, summary of adverse events, and any actions or changes with respect to the protocol. The DSM report to PCORI will also include, when available, the results of any efficacy data analysis conducted.

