**Activity 1b: Making a Plan for Side Effects and/or Cost Issues -----□**

- OK, you are having trouble taking your medicine because of... *[repeat the side effect and/or cost issue from page 4 of the Client Plan Book]*.
- Your medicine can't help you if you can't take it. Let's make a plan today to reach out to your doctor this week to see what can be done. The doctor can switch you to a different medicine, cut back the dose, or both. *Go to page 5 of the Client Plan Book. Write today's month, day, and year under "Date of plan."*
- First, let's decide who is going to call the doctor. Will you be comfortable calling by yourself? If you'd like to have somebody else on the phone with you, who will it be? *Write down who will be calling the doctor.*
- OK, now, when will you make this call? *Write down the day and time for the call.*
- Finally, let's rehearse what you'll say to the doctor. *Write down what the client will say to the doctor. Have the client repeat what they will say if they hesitate the first time.*
- OK, that sounds like we are beginning to get a plan. Let's think about how hard this may be for you to do. What are some things that might make it hard for you to carry out this plan? *Write down potential barriers.*
- What do you think you can do to overcome these things? *Help clients think of possible ways to overcome these barriers, and write down those solutions.*
- This is great. I look forward to hearing how it went when we talk next week.

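### The peer scripts for weeks 1 to 12 omit the low-sugar and low-pressure symptom check, referral and report that Safety Assessments promises

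*Combined protocol and SAP*

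**What the plan says.** Safety Assessments names the hazard: "It is possible that the interventions will result in better compliance with medication treatment, resulting in over-control of diabetes or blood pressure". For contacts during the 12-week phase it promises that "symptoms of low blood sugar and low blood pressure will be assessed and reported to the investigators", and also to the participant's physician. It adds: "If symptoms are present, the peer coach will refer participants to their primary care provider for evaluation immediately".

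The Living Well with Diabetes program description schedules peer contacts weekly in weeks 1 to 8, every two weeks in weeks 9 to 12, and monthly after that. The Peer Advisor Manual in Appendix C gives a script for each contact up to week 12, and each script carries the reminder "Cover and check off all of the session content".

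In Session 1, Activity 1a, Step 3, the peer asks about side effects of each diabetes medicine, records them, and asks whether they cause missed doses. The lead-in says "Often people can live with minor side effects". If no dose is missed, the branch reads "they are taking the medicine even though they are having a side effect), praise them and move on to Step 4" (Step 4 is the cost question). Step 6 may then send a client who has trouble with side effects to Activity 1b, where the peer proposes to "make a plan today to reach out to your doctor this week to see what can be done".

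Under Participant Retention, study staff telephone intervention participants in month 2: "Phone Call: answer questions, identify problems, update contact information".

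**The concern.** The protocol makes a specific safety commitment, and lay peers working from a script are the people who must deliver it. A peer who follows that script hears of a low-sugar or low-pressure symptom only if the client volunteers it, or names it when asked about side effects. That question is asked about diabetes medicines in week 1, and about blood pressure medicines in week 5 for some clients. Even then, no line tells the peer to refer at once or to report.

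Two groups in whom over-control is plausible are routed past medicine sections: clients who now take every dose, and clients already below 140/90. The safety board reviews quarterly reports. A low count of peer-reported symptoms could look reassuring when it only reflects that nobody was prompted to ask.

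**Working it through.** **The window.** The schedule gives 8 contacts in weeks 1 to 8, 2 in weeks 9 to 12 (weeks 10 and 12), and 3 monthly contacts (weeks 16, 20 and 24). 8 + 2 + 3 = 13, which reproduces the lower end of the protocol's stated 13 to 16 contacts. The 12-week window therefore holds 8 + 2 = 10 scheduled contacts: Sessions 1 to 6, Check-In 1 (week 7), Session 7 (week 8), Check-In 2 (week 10) and Session 8 (week 12). All ten scripts are shown. The monthly calls fall outside the window and are not counted.

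**What the ten scripts contain.**

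| Content | Scripts |
|---|---|
| Reminder to cover and tick off everything | 10 of 10 |
| Question naming low-sugar or low-pressure symptoms | 0 of 10 |
| Immediate referral for such symptoms | 0 of 10 |
| Report of such symptoms to investigators or physician | 0 of 10 |
| Open side-effect question on diabetes medicines | 1 of 10 (Session 1) |
| Branch for side-effect issues still unresolved | 7 of 10 (Sessions 2 to 8) |
| General well-being question, with no symptom branch | 5 of 10 (Sessions 1, 7 and 8, both check-ins) |
| Call to the research team within 24 hours for homework not done | 6 of 10 (Sessions 3 to 8) |

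Low blood sugar appears once, in Session 4, as a recap of what happened to someone in the video. It is not a question to the client.

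**Where the branches lead.**

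- *Session 1.* A side effect with no missed dose is met with praise. The lead-in limits itself to minor effects but does not define the word, so nothing separates a low-sugar symptom from a nuisance one.
- *Timing.* The open question is asked in week 1, before coaching can have raised adherence. That leaves 10 − 1 = 9 later contacts without it. Sessions 2 to 8 return to unresolved side-effect issues but do not ask about new ones.
- *Full adherence.* In Sessions 7 and 8 (2 of 10), a client who took every dose and has overcome all the barriers listed at the start is praised and sent past the rest of the medication section.
- *Blood pressure.* Session 5 reviews blood pressure medicines, and Sessions 6 to 8 follow up, for clients at or above 140/90 (4 of 10 scripts). A client below 140/90 skips the review in Session 5, where no lower limit is given, and is routed past the follow-up in Sessions 6 to 8. That leaves 0 of 10.

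**The case against.** The strongest objection is that the material is incomplete. Safety Assessments does not say the prompt must sit in the session scripts. It could be in the Client Plan Book (which holds the side-effect fields), the FAQs, the peers' training, or the forms for the weekly staff call to each peer. The contents list gives the manual 198 − 40 = 158 pages. Session 8's last activity starts on manual page 113, so roughly 40 pages follow that session, and only the opening of Session 9 is shown. This stands as a limit: the finding concerns the scripts shown, and the first step is to check the rest.

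The ten scripts are also not every possible contact. Appendix B mentions special calls around doctor visits, and Session 4 requires a call-back after a planned doctor call. No separate script for these is shown, so 0 of 10 describes scheduled sessions only.

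There are real partial safeguards:

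- Step 6 can lead to a doctor call within the week.
- Session 6 follows up blood pressure side-effect plans.
- Clients are taught to take side effects to the doctor, may call between sessions, and are asked to say if they feel unwell. The scripted response to feeling unwell is an offer to reschedule.
- Missed doses are discussed, but that does not reach a client who misses none.
- Session 7 asks about blood sugar, energy and mood, in terms of improvement.
- Peers take unanswered questions to the study doctors, who according to Appendix B also join the weekly group call.

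None of these is the specific question, immediate referral and report that Safety Assessments describes.

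It is fair to say that the skipped sections contain no low-sugar or low-pressure question, so skipping them loses no such check. What is lost is an occasion on which a symptom might come up. The heading of the blood pressure homework, which limits it to clients on treatment or who should discuss starting it, restricts that section and does not bring in clients routed past it.

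**Conclusion.** The concern holds. Among the ten scripts for weeks 1 to 12, none contains the symptom check, the immediate referral or the report that Safety Assessments assigns to peers at these contacts. Some stated branches lead away from detection.

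This is a gap in one monitoring layer and should be fixed. It is not an absence of monitoring. Low-sugar monitoring at follow-up in both arms, the month-2 staff call, weekly staff and coordinator contact with peers, quarterly board review, and hospitalisation and emergency data all remain. No primary analysis is affected. The documents give no rate of hypoglycaemia or hypotension, so the harm cannot be quantified. Confidence is medium, because the conclusion assumes that the unseen material does not already carry the check.

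**What to change.** First confirm whether the Client Plan Book, the rest of the manual, the FAQs, the peer training material or the Appendix G scripts already contain the check. If they do not, add one check-off line to each of the ten scripts asking about symptoms of low blood sugar and low blood pressure since the last contact, with symptom wording supplied by the investigators.

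In Session 1, place the line before the praise instruction in Step 3. In Sessions 2 to 8 and both check-ins, place it straight after the greeting, so that it precedes the medication plan and every skip in Sessions 5 to 8. A yes should trigger the referral and report already set out in Safety Assessments and be logged in a dated box like the one used for homework not done.

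The cost is one line and one box per script, brief retraining on the existing weekly peer calls, and slightly longer calls. Some false alarms will reach primary care that is already thin: Table 1 gives 1.5 to 10.1 providers per 10,000 people in the eight target counties, against 20.6 statewide.
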